## **B.** Data Points

- Gut microbiota composition: fecal samples will be collected at Days 0, 28, 56 and the day when participants recover from COVID-19-like illness (if before Day 56)
- Clinical progress of COVID-19-like illness: 1) objective and subjective symptoms data will be collected twice a day from Day 1 to Day 28 or until they recover from COVID-19-like illness (whichever is later) and once a week thereafter until Day 56 (i.e. in the mornings of Days 35, 42, 49 and 56); and 2) COVID-19-like illness severity will be assessed at Days 1, 14, 28 and 56 using the categorization from FDA [18] and the Ordinal Scale for Clinical Improvement from the World Health Organization [19]
- Proportion of participants who are "alive and not admitted to the hospital" at Days 1, 14, 28 and 56
- Proportion of participants who visit the emergency room at Days 1, 14, 28 and 56
- Outcome of COVID-19-like illness (hospitalization or death) at Days 1, 14, 28 and 56
- Glucose homeostasis if the participant has T2DM: fasting blood glucose will be measured in the mornings from Day 1 to Day 28 or until they recover from COVID-19-like illness (whichever is later) and weekly thereafter until Day 56

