To analyze the clinical data, Aalen's additive survival model will be used to test whether the impact of covarites on the cumulative hazard is time-dependent [35]. If the covariates do not vary with time, cox proportional hazards model will be subsequently used to adjust for age, gender, race/ethnicity, baseline COVID-19 severity, and whether the participant has taken treatments that may reduce COVID-19 severity (vaccination and monoclonal antibody treatment) as covariates. Survival analysis Kaplan-Meyer curves and log-rank test will be used to estimate and compare the risk of death and the risk of recovery, as a function of time, in participants with COVID-19-like symptoms [36, 37]. To compare the time to hospitalization, the time to recovery, the time to complete resolution of subjective symptoms, and the time to complete resolution of objective symptoms between treatment groups, we will use competing risks survival analysis (treating death or self-reported illness severity at Days 1, 14, 28 and 56 as a competing risk) [36, 38], use survival analysis without competing risk, and explore joint survival analysis and Bayesian survival model [39]. Specifically, cumulative incidence functions will be estimated and tested using Gray's test [40]. The Fine-and-Gray subdistribution hazard regression analysis [38] will be used to further adjust for age, gender, race/ethnicity, baseline COVID-19 severity, and whether the participant has taken treatments that may reduce COVID-19 severity (vaccination and monoclonal antibody treatment) as covariates. Proportion of participants who are "alive and not admitted to the hospital", proportions of participants who visit the emergency room at Days 1, 14, 28 and 56, have complete resolution of objective symptoms, have complete resolution of subjective symptoms and have complete resolution of subjective symptoms except cough and fatigue at Days 1, 14, 28 and 56 will be compared between groups using separate logistic regression analysis at each time point. Time for participants to have complete resolution of objective symptoms, complete resolution of subjective symptoms and complete resolution of subjective symptoms except cough and fatigue will be compared between groups using competing risks survival analysis described previously, treating death or self-reported illness severity at Days 1, 14, 28 and 56 as a competing risk [36, 38]. To compare the longitudinally (repeatedly) measured illness severity based on the Ordinal Scale for Clinical Improvement from the World Health Organization, body temperature (oral), oxygen saturation level, pulse rate, respiratory rate and fasting blood glucose between treatment groups, accounting for the effect of death, reported adverse event, or other appropirate competing risk, we will compare the treatment effect using the method of joint survival and longitudinal data analysis [41, 42], where each of the clinical outcomes (e.g., illness severity, body temperature (oral), and oxygen saturation level, etc.) will be modeled using linear mixed models, and death, reported adverse event, or other appropirate competing risk will be modelled using Weibull proportional hazards model [43]. Age, gender, race/ethnicity, baseline COVID-19 severity, and whether the participant has taken treatments that may reduce COVID-19 severity (vaccination and monoclonal antibody treatment) will be controlled as covariates in these statistical analyses, where appropriate. Within-group changes of main outcomes between groups will be modeled as change from pre- to post-treatment using ANOVA and modeled as the post-treatment value as the change itself with the pretreatment value entered as covariate using ANCOVA [44]. Lastly, alternative statistical methods will be explored to quantify the underlying differences between groups with respect to a time-to-event end point, robust methods include calculating ratio/difference of t-Year Survival Rates, ratio/difference of percentiles of survival functions, and ratio/differenceof restricted mean survival times or restricted mean time lost [45]. Statistical analyses described above will be conducted for both intent-to-treat dataset and per-protocal dataset. For each test of an outcome, we define the statistical significance by p<0.05. The false discovery rate [46] will be applied for multiple testing, where appropriate. Sensitivity analysis using multiple imputation methods [47] will be performed to handle the missing data. Other

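### Self-reported illness severity is named as a competing risk for recovery, symptom resolution and admission, although it precludes none of them and no rule turns a rating into a dated event

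*Protocol*

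**What the plan says.** Protocol section 6.1 and the SAP's Clinical Data Analysis use the same wording, twice in each document. Time to hospitalization, recovery, and subjective and objective symptom resolution are to be analysed by competing-risks methods, "treating death or self-reported illness severity at Days 1, 14, 28 and 56 as a competing risk", with Gray's test and covariate-adjusted Fine-Gray regression. Resolution apart from cough and fatigue follows by cross-reference: "complete resolution of subjective symptoms except cough and fatigue will be compared between groups using competing risks survival analysis described previously".

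Other analyses do not use this event:

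- For the first four endpoints the plan will also "use survival analysis without competing risk, and explore joint survival analysis and Bayesian survival model".
- "Survival analysis Kaplan-Meyer curves and log-rank test will be used to estimate and compare the risk of death and the risk of recovery".
- Section 6.1 opens with an Aalen model followed, if appropriate, by a Cox model, without naming an endpoint.
- The resolution, hospital-free and emergency-room proportions "will be compared between groups using separate logistic regression analysis at each time point".
- Contrasts such as "restricted mean survival times or restricted mean time lost" are to be explored.

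None of the time-to-event analyses is called the main one.

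On severity itself, Protocol 1.3 B says that "COVID-19-like illness severity will be assessed at Days 1, 14, 28 and 56", using FDA categories and the WHO ordinal scale. Protocol 1.3 D lists that rating as secondary endpoint (g). Separately, under Sample and Data Collection in 1.3 A, participants grade each symptom themselves.

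**The concern.** A competing event is one after which the target event can no longer happen. Death qualifies for recovery. Being rated as ill does not: illness is the state from which people recover, resolve or are admitted.

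There are two separate defects. First, the event cannot be coded from the text supplied. A statistician would need a qualifying level or change, a first-or-any-occurrence rule, a date and a data source, and only the assessment days are stated. Second, even a fully specified threshold would be the wrong kind of event. In Gray and Fine-Gray analyses a participant coded as competing never contributes a later recovery, so recovery incidence is understated. The same applies to admission after a qualifying rating.

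Treatment may itself affect severity. If the coded share differs by arm, one trial outcome then removes events from another, and a difference in severity can appear as a difference in recovery. Because no time-to-event analysis leads, nothing decides between the competing-risk result and the others if they disagree.

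**Working it through.** **Setting the passages side by side**

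- *Level and date.* Section 6.1 and the SAP give Days 1, 14, 28 and 56. These are the visits at which the 1.3 B rating is made. Neither document gives a level, a direction of change or an event date.
- *Source.* The shared days point to the 1.3 B rating, but that section does not call it self-reported. The grades participants give themselves in 1.3 A are per symptom. The supplied text ties the phrase to neither.
- *Does it preclude the outcome?* Under Interventions in 1.3 A, hospitalized participants stay in follow-up to Day 56. Under Sample and Data Collection they give a stool sample after recovering and keep diaries after discharge until recovery. The protocol therefore expects recovery even after admission.
- *Role elsewhere.* Severity is endpoint (g), and in the joint model it is a longitudinal outcome.

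**Effect on incidence.** The plan has no figure to reproduce here. The sample size in 1.5 rests on PERMANOVA. The following assumptions are not in the documents: exponential recovery with median m, no deaths, complete follow-up, and a share f of those unrecovered at Day 14 coded as competing.

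F(t) = 1 − exp(−ln 2 × t/m)

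Reported Day 28 value = F(14) + (1 − f) × [F(28) − F(14)]

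For m = 14, F(14) = 0.50 and F(28) = 0.75:

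- f = 0.10: 0.50 + 0.90 × 0.25 = 72.5%
- f = 0.50: 0.50 + 0.50 × 0.25 = 62.5%

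| Median (days) | True Day 28 | f = 0.10 | f = 0.50 |
|---|---|---|---|
| 7 | 93.8% | 91.9% | 84.4% |
| 10 | 85.6% | 83.3% | 73.9% |
| 14 | 75.0% | 72.5% | 62.5% |
| 18 | 66.0% | 63.5% | 53.8% |

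The understatement is f × [F(28) − F(14)]. With m = 14 and identical recovery, f = 0.50 in one arm and 0.10 in the other gives 62.5% v 72.5%, an apparent gap of 10 points.

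**Effect on Gray's test.** This was simulated as a log-rank test on subdistribution times, with coded participants kept at risk to Day 56. There were 50 per arm (Protocol 1.5), identical recovery in both arms and coding at Day 14. The level was two-sided 5%; section 6.1 gives p<0.05 without sidedness. The 14-day column uses 6,000 runs (simulation error 0.3 to 0.6 points) and the other two use 4,000.

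| Coded shares | Median 7 | Median 10 | Median 14 |
|---|---|---|---|
| 10% v 5% | 6% | 6% | 6% |
| 25% v 10% | 6% | 8% | 9% |
| 50% v 25% | 8% | 10% | 15% |
| 50% v 10% | 13% | 23% | 32% |

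With equal shares at a 14-day median, rejection stays at 5.1% to 5.4%. A repeat of the bottom row gave about 12.5%, 23% and 33%, hence the range of 12% to 33%. At a 14-day median, other assumptions move the 50% v 10% figure further: 36% with coding at Days 14 and 28, 41% if no recovery is possible before Day 5, and 15.5% with 20 per arm.

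**The case against.** Several points on the other side have force.

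- *The text does give times.* It names four days, so it would be too strong to say that the event has no time at all. What is missing is the rule that turns a rating on those days into a dated event.
- *A definition may exist elsewhere.* The reporting forms (Appendices 9 to 11) were not supplied and may explain what is self-reported. The point about definition is therefore limited to the supplied text.
- *Worsening was probably meant.* Baseline severity is a covariate, which suggests the authors had deterioration in mind. That is plausible, but a worsening threshold cures only the coding problem. Participants who worsen can still recover.
- *Recovery without worsening is a legitimate target.* If severity differs by arm, that quantity really does differ, and a rejection is not a false positive for it. This stands. The defect is that the plan presents the analysis as one of recovery.
- *Unaffected analyses are planned.* This also stands, and it limits the damage. They are unranked, however, and time to resolution apart from cough and fatigue is not in the list given an analysis without competing risk.

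A reader might go further and infer that every participant has the competing event at Day 1, since all enter with mild or moderate illness. The inclusion criteria in 4.1 C describe severity at screening. The Day 1 rating is not given, and the illustration does not use this reading. A reader might also infer that hospitalized participants leave the risk set. Nothing says so, and 1.3 A keeps them in follow-up.

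**Conclusion.** The competing-risk rule is wrong as written, not merely under-described: it names a state that does not preclude the outcomes. That conclusion rests on the text alone and needs no numerical assumption. The direction of the incidence error is also clear: any participant coded as competing who later recovers is lost from the recovery curve.

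The size is not established. The documents give neither the coding nor recovery rates, and nothing in them supports a contrast as wide as 50% v 10% between arms with identical recovery. With small or equal shares the test is hardly disturbed; with large unequal shares it is disturbed materially. No conclusion about power is drawn, because the effect depends on who is coded.

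A reader might infer that the trial's main result is compromised. It is not. The primary outcome is gut microbiota composition, its sample size is unaffected, and Protocol 1.1 frames the study as one of feasibility and exploration. The point concerns secondary clinical endpoints, each of which is still tested at p<0.05, and it should be fixed on that footing.

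**What to change.** Amend Protocol section 6.1 and the SAP's Clinical Data Analysis together:

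1. Remove self-reported illness severity as a competing event. Use death as the competing event for recovery and symptom resolution, and death before admission for hospitalization. Keep baseline severity as a covariate and severity as endpoint (g).
2. If recovery without prior worsening is of interest, report it as a separately named estimand, with the worsening level, the data source and the event date defined.
3. Name one main time-to-event analysis for each clinical endpoint, including resolution apart from cough and fatigue, and label the others as sensitivity analyses.

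The cost is wording in two documents, with no new data collection. The change should be made before outcomes by arm are examined, because the choice of coding could by itself alter a result.

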INFORMED CONSENT AND ELIGIBILITY SCREENING PART 2. The informed consent process will be conducted via Castor's eConsent video call module. At the beginning of the call, the study coordinator will confirm that the study candidates continue to experience the COVID-19-like symptoms reported in the preliminary screening survey, thereafter the study coordinator will explain the rationale, aim, expected outcomes and significance of the research, the experimental procedures, what is required from the participants, and the benefits and risks associated with the study. Electronic informed consent will be obtained during the interview prior to further eligibility screening (Appendices 3 and 4). A consent for health information release (Appendix 3) will also be obtained during informed consent procedure. After the study candidates sign the electronic informed consent documents, the study coordinator will ask some additional questions regarding their medical history and other conditions to establish eligibility (Appendix 4). In the case of study candidates who are recruited online, they will also be asked to provide electronic proofs of a positive/pending COVID-19 test (Appendix 24) and a negative pregnancy test result (if appropriate; Appendix 6) during the interview. This consent and eligibility screening interview will take a maximum of 60 minutes to complete.

**ENROLLMENT.** The study physicians will review all screening data and determine if the study candidates are suitable for home isolation and confirm enrollment.

**RANDOMIZATION AND ALLOCATION CONCEALMENT.** Enrolled participants will be randomized to the control or treatment group at a 1:1 ratio, using randomization via a dynamic minimization to minimize imbalance between groups over factors including COVID-19-like illness severity (mild vs moderate), the use of COVID-19 vaccination or other treatments that may reduce severity such as monoclonal antibody treatment vs. not used, age (≤60 vs >60 years) and gender (male vs female) [16]. When imbalance is detected, the new patient will be allocated with probability 0.7 vs 0.3. When the treatment assignments are at balance, the patient will be allocated with probability 0.5 vs 0.5. The randomization will be performed

via a closed source app written by one of the Co-PI. The investigator who uses the app will only know the allocation result, i.e., control or treatment group, of the new patient.

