## 1.5 Sample Size Justification

We will enroll a total of 100 participants who have COVID-19-like symptoms and have positive/pending PCR-based COVID-19 test results. These individuals will be randomized into the control and treatment group in a 1:1 ratio (i.e. 50 participants/group). With the assumption of a positivity rate of 40-50% in symptomatic participants in the USF Carol & Frank Morsani Center for Advanced Healthcare drive-through testing center, we expect to have at least 20 confirmed COVID-19 cases in each group. We used the micropower R-package [27], in which the weighted Jaccard distance matrix was simulated based on within-group distance variance (mean and standard deviation) of data from 36 T2DM patients (unpublished data) to estimate the required sample size. Using the simulated matrices, the PERMANOVA powers are calculated for varying effect sizes ( $\omega^2$ ) and sample sizes. Our results show that 16 subjects per group afford 80% power to an  $\omega^2$  of 0.0106 which correspond to the difference ( $\omega^2$ =0.0120) between the control and treatment group with a similar high-fiber intervention in the T2DM patients (unpublished data). We therefore aim to recruit 20 confirmed COVID-19 cases in each group to allow for potential dropouts and/or incomplete sample/data sets from the participants.

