# C. Feasibility

There are over 2,000 new COVID-19 cases every day in Florida. Around 100 individuals attend the USF Carol & Frank Morsani Center for Advanced Healthcare drive-through testing center for COVID-19 testing each day and among the confirmed cases the prevalence of diabetes is 12%. We therefore consider this patient flow sufficient for recruiting the targeted number of subjects in the specified duration.

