# E. Minimizing Risks of Harm

Participants will be provided with oral and written instructions and supplies to collect fecal samples at home without direct physical contact with the specimens throughout the process. The specimens will be stored in a sealed container, a leak-proof secondary package (a sealable plastic bag lined with absorbent pads) and an outer package (e.g. a shipping box). Participants are not required to store the samples at home; they will mail the specimens to the research team using the shipping supplies provided.

To minimize adverse effects due to NBT-NM108, participants in the treatment group will be asked to gradually increase the dose to avoid adverse events associated with an acute increase in fiber intake. They will also be advised to drink enough fluids throughout the study including the amount of water taken together with NBT-NM108) to avoid constipation. Participants will be asked to monitor potential adverse events daily. If participants report an adverse event, a member of the study team will contact them to ask follow-up questions about the degree of severity (mild, moderate, or severe) and the frequency of the adverse events. The study physician (co-PI [name]) will assess the adverse events and, if necessary, she will instruct the participants to reduce the consumption of NBT-NM108 to a lower dose that has been tolerated, and so on. If the same level of discomfort continues i.e.. for three consecutive days, the treatment will be discontinued. Participants are also at asked to closely monitor their blood glucose level and discuss with their family physicians about adjusting their medications to prevent hypoglycemia.

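### Fasting glucose is measured only in participants with T2DM, about 12 people on the protocol's own figure, but is assigned the same adjusted joint model and p<0.05 rule as outcomes measured in everyone

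*Protocol*

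**What the plan says.** Protocol 1.3 D (Endpoints) lists fasting blood glucose as a secondary outcome at Days 1, 14, 28 and 56, with no restriction on who contributes. Protocol 1.6 B leaves it out of the outcome list altogether. The restriction appears in 1.3 B: "Glucose homeostasis if the participant has T2DM". Sections 1.3 A and 1.9 A say the same.

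Protocol 6.1 and the SAP's Clinical Data Analysis section name "body temperature (oral), oxygen saturation level, pulse rate, respiratory rate and fasting blood glucose between treatment groups", together with ordinal illness severity, for a joint longitudinal and survival analysis. The outcome part is a linear mixed model. The event part is a Weibull model. Age, gender, race/ethnicity, baseline severity, and vaccination or monoclonal antibody treatment are covariates where judged suitable. The error rule is "For each test of an outcome, we define the statistical significance by p<0.05", with false discovery rate control conditional in the same way. All of this is run in both the intent-to-treat and per-protocol sets.

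On numbers, section 1.5 says "We will enroll a total of 100 participants who have COVID-19-like symptoms", and 4.3 C says that "among the confirmed cases the prevalence of diabetes is 12" percent. Allocation is 1:1 by minimization (1.3 A), and diabetes is not among its factors.

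**The concern.** A model specification that suits about 100 participants is applied unchanged to an outcome that perhaps 12 will have. Daily readings add observations but not participants, and a comparison of average glucose between arms is limited by the number of participants. With that few, seven or eight participant-level parameters use up most of the information on the arm effect. A large-sample test then treats the estimated variance as known, and its p-values come out too small. The risk is a glucose effect reported on p<0.05 that is an artefact of the test. Leaving the covariate set open makes this worse, because at this size the choice of covariates can decide the result.

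**Working it through.** **The plan's own figures.** Neither document gives a sample size, power or error rate for glucose. The sample-size section concerns the microbiota outcome. Its 20 confirmed cases per group follow from 50 × 0.40 = 20. Its 16 per group cannot be recomputed, because the distance variances are unpublished. Neither figure bears on glucose.

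**Number with glucose data.** 100 × 0.12 = 12, or 6 per arm. A binomial(100, 0.12) count has a 95% range of 6 to 19, and P(count ≤ 8) = 0.139. Counting confirmed cases only, (40 to 50) × 0.12 = 4.8 to 6.

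**Parameters.** There is an intercept, the arm, and five single-degree-of-freedom covariates if vaccination and antibody treatment share one indicator and race/ethnicity is binary: p = 7. With separate indicators, p = 8. More race/ethnicity levels raise p further.

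**False-positive rate.** Take a time-averaged arm effect in a balanced random-intercept model with n participants and df = n − p:

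- REML variance, z reference: 2·P(t_df > 1.96)
- ML variance, z reference: 2·P(t_df > 1.96·√(df/n))
- t reference on df: 5%

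For n = 12 and p = 8, df = 4. REML gives 2·P(t₄ > 1.96) = 0.122. For ML, 1.96·√(4/12) = 1.132 and 2·P(t₄ > 1.132) = 0.321.

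| n | p | df | REML, z | ML, z |
|---|---|---|---|---|
| 12 | 2 (arm only) | 10 | 7.8% | 10.4% |
| 12 | 7 | 5 | 10.7% | 26.2% |
| 12 | 8 | 4 | 12.2% | 32.1% |
| 19 | 8 | 11 | 7.6% | 16.4% |
| 100 | 8 | 92 | 5.3% | 6.3% |

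A simulation with 28 daily values, an assumed intraclass correlation of 0.6 and 6,000 runs per setting agrees. It gave 10.8% and 26.2% (n = 12, p = 7), 12.4% and 32.4% (n = 12, p = 8), and 5.2% and 6.3% (n = 100, p = 8). With a t reference the simulated rate at n = 12 was 4.9% to 5.3%. The problem is therefore confined to the outcome measured in few people.

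**Feasibility of the fit.** At n = 8 with p = 8, df = 0. At n = 7 the mean model cannot be fitted.

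**Precision.** With 6 per arm and a two-sample t test, 80% power needs a difference of 1.80 SD of a participant mean. With eight mean parameters it needs about 2.2 SD, assuming the covariates explain no variance and are unrelated to arm.

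**The case against.** A reader might infer that the planned glucose test has a false-positive rate of up to 32% as a matter of fact. The documents do not support that. They name neither ML nor REML and neither a z nor a t reference, and a t reference on residual degrees of freedom holds about 5%. They do not say whether the treatment effect is a main effect or an arm-by-time effect. For a random-slope arm-by-time effect with five covariates, a smaller simulation (624 runs, some convergence warnings) gave only 7.9% (REML z) and 9.9% (ML z). The covariates are not mandatory either. The 12% is any diabetes among confirmed cases at one center, while the trial also takes pending cases and recruits nationally. All of this stands, and it makes the size of the error conditional.

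It does not remove the point. The named method is a likelihood-based joint model with a cited joint-model R package, so large-sample inference is the natural reading. ANCOVA with the pretreatment value appears in the same section, but only for main outcomes that are never defined.

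Two further inferences also go too far. Section 4.7 E asks participants to "discuss with their family physicians about adjusting their medications to prevent hypoglycemia", and a reader might conclude that any glucose effect is uninterpretable. Medication changes are recorded, however, and an effect that includes them is a legitimate estimand. Nor does the small number require dropping every test, since a suitable test controls the error. That glucose is one secondary outcome among many in a feasibility study is fair, and it limits the importance of the point.

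**Conclusion.** The concern holds in conditional form. The documents establish that glucose is restricted to T2DM, that it is analysed like the outcomes measured in everyone, and that no T2DM analysis set, reduced covariate list or small-sample reference is given. The count of about 12 (range 6 to 19) is an assumption carried over from the single-center diabetes figure.

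The 11-12% (REML) and 26-32% (ML) rates need three conditions together: a time-averaged arm effect, a Wald z test, and five or six single-degree-of-freedom covariates. Without covariates the rates fall to about 8-10%. At the favourable end of the range (19 participants, eight parameters) they are 7.6% and 16.4%. Even with a correct reference, only very large differences are detectable. The change should be made because a better method is available at almost no cost, but it does not affect the trial's primary conclusion.

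**What to change.** In Protocol 1.3 D, Protocol 6.1 and the SAP's Clinical Data Analysis section:

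- State that fasting glucose is analysed in participants with T2DM only and is exploratory.
- For this outcome, replace the joint model with one value per participant: mean post-baseline fasting glucose over a stated window. Compare arms with arm and baseline glucose as the only terms. Use a t reference on residual degrees of freedom (12 − 3 = 9 at the expected count) or a permutation test.
- Define baseline. Readings and study drinks both start on Day 1, so say whether the Day 1 fasting reading precedes the first drink.
- Report the estimate with its confidence interval and the number per arm, beside diabetes-medication changes by arm, which are already collected.
- Reconcile the outcome lists in 1.3 D and 1.6 B.

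The cost is wording only; no data collection changes. The downside is that glucose leaves the common joint-model framework, with its handling of death and other events, and loses its other covariates. The comparison stays imprecise: about 1.8 SD of a participant mean at 6 per arm, before any gain from baseline adjustment.
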